Total Complications	31.05%	50%	95.65%	100%
---------------------	--------	-----	--------	------

The sample size was calculated using the openepi web tool, available at: https://www.openepi.com/Menu/OE_Menu.htm. To approximate to a round number the sample calculation, it was used the Cohorts option, considering the unexposed group as the classification option with the lowest percentage of total complications (T1), and the exposed group as the classification option with the highest percentage of total complications (T4). With a confidence level of 95%, power of 80%, ratio of unexposed/exposed = 1, percentage of unexposed positives = 31.05% and percentage of exposed positives = 99.99%; the following results are obtained.

Tamaño muestral: transversal, de cohorte, y ensayo clínico

Nivel de significación de dos lados(1-alpha)	95
Potencia (1-beta,% probabilidad de detección)	80
Razón de tamaño de la muestra, Expuesto/No Expuesto	1
Porcentaje de No Expuestos positivos	31
Porcentaje de Expuestos positivos	100
Odds Ratio:	22000
Razón de riesgo/prevalencia	3.2
Diferencia riesgo/prevalencia	69

	Kelsey	Fleiss	Fleiss con CC
Tamaño de la muestra - Expuestos	8	7	9
Tamaño de la muestra- No expuestos	8	7	9
Tamaño total de la muestra	16	14	18

It is expected that as we progress through the 7 option types of the proposed classification, we will have fewer patients; this implies that the classification with the lowest recruitment expectation will be T5b. All logistic efforts and recruitment strategies will be made to obtain at least 9 patients in the least frequent option type, considering the Fleiss sample size on continuous adjustment. Due to the difficulty of obtaining a significant and similar number of patients on each option type, it is considered appropriate to include all cases of PAS who visit the participating centers and meet the admission criteria in the 2-year period, with the possibility of extension, if the minimum number of cases for each option

Data collection techniques

The group of obstetrician-gynecologists will inform the principal investigator or study coordinator about patients that can be included in the study. Once it is confirmed that they meet the inclusion criteria, the data will be collected from the electronic or paper-based medical records of the hospital, protecting the identity of the patients at all times.

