In both cases, the null hypothesis (H_0) indicates that the mean or median numbers of the 7 subpopulations are equal; the alternate hypothesis (H_a) refers to the above being different. If the p-value indicated by those tests is ≥ 0.05 (5%), it can be stated that there are no statistically significant differences between the mean or median numbers of the 7 subpopulations, with 95% confidence, which is set for the study. If the p-value is < 0.05 , the hypothesis of having no difference in the mean or median numbers (H_0) is rejected. That does not imply that a particular subgroup is superior or inferior to another.

For qualitative variables, a statistical test of the difference in proportions of the 7 subgroups (independent groups) will be performed by means of the Chi-square test. A result with a p-value ≥ 0.05 (5%) can be interpreted as: the proportions of the variable in question do not differ, in terms of statistical significance, among the seven groups. In case the p-value is < 0.05 indicates that there are statistically significant differences between at least two of the seven groups with respect to the proportions of the variable addressed. This does not imply that a particular subgroup is superior or inferior to another.

The results are shown in Table 3.

Specific Objective 2: To analyze the clinical outcomes of patients diagnosed with placenta accreta spectrum according to anatomical classification.

Descriptive Analysis: Stratification by subgroups will be performed according to the anatomical classification of PAD as follows: T1, T2a, T2b, T3, T4, T5a and T5b. Qualitative variables will be summarized as percentages and presented as absolute frequencies. For quantitative variables, the normality distribution will be determined by means of the Kolmogorov statistic.

Smirnov (sample size greater than 50 patients is expected), where a result of p-value >0.05 would comply with the assumption of normality. For variables with normal distribution, mean and standard deviation will be determined; and for variables without normal distribution, median and interquartile ranges (Q1 - Q3) will be indicated.

Inferential Analysis: For quantitative variables, a statistical test of the difference in means of the 7 subgroups (independent groups) will be performed by means of one-way ANOVA for independent groups. If the variable does not have a normal distribution, the Kruskal-Wallis test will be performed.

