In both cases, the null hypothesis (H_0) indicates that the means or medians of the 7 subpopulations are equal; the alternate hypothesis (H_a) refers to the above being different. If the p-value indicated by these tests is ≥ 0.05 (5%), it can be stated that there are no statistically significant differences between the means or medians of the 7 subpopulations, with 95% confidence, which is set for the investigation. If the p-value is < 0.05 , the hypothesis of equality of population means or medians (H_0) is rejected. This does not imply that a particular subgroup is superior or inferior to another.

For qualitative variables, a statistical test of the difference in proportions of the 7 subgroups (independent groups) will be performed by means of the Chi-square test. A result with a p-value ≥ 0.05 (5%) can be interpreted as: the proportions of the variable in question do not differ in terms of statistical significance, among the seven groups. In case the p-value is < 0.05 , it indicates that there are statistically significant differences between at least two of the seven groups with respect to the proportions of the variable been assessed. That does not imply that a particular subgroup is superior or inferior to another.

The results are shown in Table 4.

Specific Objective 3: To explore the acceptability of the topographic classification of

placenta accreta spectrum among obstetrician-gynecologists at the participating medical centers.

In the scientific literature there is no validated scale to evaluate the acceptability of a new clinical classification, which in this case is proposed as a topographic classification of PAS. After an exhaustive search, it was concluded that the *The Ottawa Acceptability of Decision Rules Instrument* would be utilized, which is a widely used instrument to evaluate the acceptability of a norm among physicians. There is no linguistic adaptation to Spanish, so a direct translation of its content was made.

After the principal investigator had reviewed it, was necessary make adaptations to some items, which were:

- a) Change the original term "norm" to "*anatomical classification for PAS*". In all items.

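### For quantitative variables the plan attaches 95% confidence to a non-significant result; 1 − alpha gives no such assurance, and no difference estimate or confidence interval is planned to show what the data leave open

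*Combined protocol and SAP*

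**What the plan says.** The point concerns the Inferential Analysis paragraphs under Data Management and Statistical Analysis.

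- **Quantitative variables (one-way ANOVA or Kruskal-Wallis).** If p ≥ 0.05, the Objective 2 text says "it can be stated that there are no statistically significant differences between the means or medians of the 7 subpopulations, with 95% confidence". The Objective 1 text reads the same way: "there are no statistically significant differences between the mean or median numbers of the 7 subpopulations, with 95% confidence, which is set for the study".
- **Qualitative variables (chi-square).** If p ≥ 0.05, the Objective 2 reading is that "the proportions of the variable in question do not differ in terms of statistical significance, among the seven groups"; Objective 1 has the same sentence. Neither mentions 95% confidence.
- **p < 0.05.** Both objectives warn that a significant result does not make any one subgroup superior or inferior. There is no matching caution for p ≥ 0.05.
- **What is reported.** Frequencies and percentages, mean and SD, or median and quartiles, for each type. Table 4 adds one p-value column. No difference between types and no confidence interval is planned.
- **Sample size.** The calculation compares T1 with T4: "With a confidence level of 95%, power of 80%, ratio of unexposed/exposed = 1", with "percentage of unexposed positives = 31.05% and percentage of exposed positives = 99.99"%. The resulting 9 is a minimum for the least frequent type. All eligible cases over two years are enrolled in the other types.

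**The concern.** A 95% level for a test means that, when the groups are truly alike, the test stays non-significant 95% of the time. It is not the confidence one may have in a non-significant finding. That depends on how often the test would also be non-significant when the groups differ, which is 1 − power. The plan transfers the figure from the first quantity to the second, and does so in a reading rule set in advance and used for two objectives.

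The research question is whether the topographic type is useful in determining clinical outcomes. A non-significant comparison of, say, blood loss reported with 95% confidence could be taken as reassurance that the types carry similar risk. With no interval beside it, nothing in the planned tables would show how large a difference the data still allow.

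**Working it through.** **Inputs from the protocol (Sample size and sampling strategy).** Two-sided alpha 0.05; power 80%; ratio 1:1; cited total complications T1 31.05%, T2 50%, T3 95.65%, T4 100% (entered as 99.99%); cited group sizes 248, 44, 23 and 11; floor of 9 in the rarest type. The documents give no SD, no rates for individual complications and no T5 rates, so those below are assumptions.

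**1. The plan's own figure.** With p1 = 0.3105, p2 = 0.9999, d = 0.6894 and mean p = 0.6552:

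- Fleiss: n = [1.960·√(2·0.6552·0.3448) + 0.842·√(0.3105·0.6895 + 0.9999·0.0001)]² / 0.6894² = 6.13, so 7.
- With continuity correction: (6.13/4)·[1 + √(1 + 4/(6.13·0.6894))]² = 8.79, so 9.
- Kelsey: (1.960 + 0.842)²·2·0.6552·0.3448 / 0.6894² = 7.46, so 8.

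All three agree with the protocol (8, 7 and 9 per group).

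**2. What 9 against 9 can detect** (normal approximation; exact uncorrected chi-square)

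| Pair, cited rates | Power |
|---|---|
| T1 vs T4 | 95%; 97% |
| T1 vs T3 | 88%; 92% |
| T1 vs T2 | 12%; 13% |

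For T1 vs T2 the Fleiss formula with d = 0.1895 gives 104.2, so 105 per group for 80% power. Starting from 31.05%, 9 against 9 reaches 80% power only when the other rate is about 92%.

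**3. The planned seven-group chi-square** (simulation, 6 df)

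At the cited rates, with 2U and 2L both at 50% and both T5 types assumed at 31%, power is about 99% with 9 in every group.

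Two assumed scenarios with smaller differences: (A) 50% in 2U and 2L, 31% elsewhere; (B) 20% in 2L, 3, 4 and 5L, 10% elsewhere. The last row scales the cited series to T4 = 9: 248·9/11 = 203, 44·9/11 = 36 (split 18 and 18), 23·9/11 = 19, with both T5 types assumed at 9.

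| Sizes T1/2U/2L/3/4/5U/5L | A | B |
|---|---|---|
| 9 in each | 13% | 8–9% |
| 60, then 9 in each | 18% | 22% |
| 150, then 9 in each | 20% | 31% |
| 203/18/18/19/9/9/9 | 35% | 38% |

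**4. ANOVA, the setting in which the 95% phrase appears.** Power comes from the noncentral F distribution with λ = Σ nᵢ(μᵢ − μ̄)²/σ². If one type of size 9 is shifted by δ SD, λ = 9·δ²·(1 − 9/N).

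- N = 7·9 = 63, δ = 0.5: λ = 2.25·(1 − 9/63) = 1.93, df 6 and 56, power 13%.
- Assumed unequal split 120/20/12/12/9/9/9, N = 191, δ = 0.5: λ = 2.25·(1 − 9/191) = 2.14, df 6 and 184, power 15%.
- δ = 1.0: 46% and 55%. δ = 1.5: 86% and 92%.

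So with a true 0.5 SD shift in one rare type, the statement carrying 95% confidence would be made in 1 − 0.15 = 85% to 1 − 0.13 = 87% of studies.

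**5. What an interval would add.** Suppose 3/9 in one type and 5/9 in another. The chi-square p is 0.34. The difference is 22 percentage points, with a Newcombe 95% interval from −20 to +55. The p-value would be reported as not significant; the interval shows that the comparison settles nothing.

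**The case against.** The best defence is that the plan is more careful than a quick reading suggests, and most of it stands.

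- A reader might infer that the plan equates p ≥ 0.05 with no difference between types. It does not. Both readings keep the qualifier of statistical significance, and nowhere are the types called equal or equivalent. Without the 95% phrase, the sentences only restate a non-significant test.
- A reader might extend the 95% error to every test. It is confined to the ANOVA and Kruskal-Wallis text. The chi-square figures in step 3 bear on the missing intervals, not on that phrase.
- A reader might take 9 as the size of all groups. It is a floor for the rarest type, and the Theoretical Framework calls type 1 the most frequent, so equal groups of 9 are the pessimistic end.
- A reader might infer that power is low throughout. For total complications, the only outcome whose rates the documents give, it is about 99% under the stated T5 assumption.
- A reader might say that the p-value is all that is reported. Per-type counts, percentages and summaries are also planned, and an interval could be derived from the counts.

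What survives is the phrase itself, which nothing elsewhere in the plan corrects, and the absence of any planned interval.

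**Conclusion.** The concern holds as a defined error of interpretation together with a reporting gap. Attaching 95% confidence to a non-significant ANOVA or Kruskal-Wallis result is wrong whatever the power. It matters in practice because power, although high for the large contrasts the plan cites, is about 9% to 38% for the assumed moderate or rarer differences in proportions, and about 13% to 15% for a 0.5 SD shift in one type. Those ranges rest on assumed rates, effect sizes and group splits, with the rarest types at 9; larger rare groups or larger effects would raise them. That the investigators would go on to claim that the types do not differ is a possible misreading of the results, not something the plan states. The test choices and the sample size calculation are not called into question by this point.

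**What to change.** 1. Under Objectives 1 and 2, delete the 95% confidence phrase from the reading of p ≥ 0.05 for quantitative variables.
2. State once, for all tests, that p ≥ 0.05 is inconclusive unless the confidence interval excludes a difference that matters. Name that difference for the main outcomes before the analysis.
3. For Objective 2, give in Table 4 each type's proportion or mean with a 95% interval, and its risk or mean difference from T1 with a 95% interval. Where medians are reported, give the median difference and its interval. Blood loss in millilitres, a quantitative Objective 2 outcome in the Table of Variables, appears in Table 4 only as haemorrhage stages and would need its own row.

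The cost is a few sentences and the added table entries. Conclusions become more cautious. No test, sample size or data collection changes.

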 Exclusion criteria	14
Data collection techniques	16
Data Management and Statistical Analysis	16
Table of Variables	19
Blank Tables	23
OPERATIONAL ASPECTS	28
SOCIALIZATION OF RESULTS	29
ETHICAL CONSIDERATIONS	29
SCHEDULE	33
REFERENCES	35
ANNEXES	38

INTRODUCTION

The incidence of placenta accreta spectrum (PAS) has hiked up, directly proportional to the increased frequency of cesarean section (1). As the name implies, the condition includes a spectrum of various clinical presentations, from "mild" forms, which if managed by expert groups can have intraoperative risks similar to cesarean section; to very severe forms that can lead to death and require both great surgical skill and the use of multiple healthcare resources (2).

The classification of PAS adopted by the International Federation of Gynecologists (FIGO) is based on the degree of penetration of the placenta into the myometrium. Therefore, its histologic staging is only possible by analyzing a tissue sample after surgery and does not contribute to surgical decisions. In addition, histological analysis is seldom available in center with limited resources (3).

Among the characteristics expected to be found in a classification applied for a disease that is managed surgically, its application prior to surgery (based on imaging studies) and its confirmation during laparotomy, are ideal. Additionally, such a classification should make it easier to choose the treatment option and correlate with the clinical results or the degree of surgical difficulty. An interesting proposal for PAS is the topographic classification created by [name] et al (1), with 5 differentiated categories based on the part of the uterus affected and the possibility of separating or not the uterus from the bladder. This classification has been studied and successfully implemented by hospitals in low- and middle-income countries, and retrospective studies have been carried out describing its correlation with clinical results and the usefulness of one or another surgical technique (1,4). Currently there are no prospective multicentric studies that address the relationship between this anatomical classification with clinical variables, and no study has reviewed the opinions of the professionals who use it.

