We propose the execution of a prospective multicentric study consisting of a cohort of patients with prenatal or intraoperative diagnosis of PAS, evaluating the clinical outcomes of the group of patients found in each category of the topographic classification. In addition, an approach to evaluate the acceptability of this classification among the obstetrician-gynecologists of the participating medical centers will be included.

THEORETICAL FRAMEWORK

Definition

Traditionally, PAS has been considered to be due to an abnormal insertion of the placenta, when the chorionic villi abnormally invade the myometrium (5). However, recent publications emphasize the non-invasive nature of placentation in PAS. The fundamental problem is the presence of an established myometrial defect in the uterus prior to pregnancy, clearly linked to previous surgical trauma, been history of cesarean section the main risk factor. When the placenta implants over that defect, as is the case of placenta previa in women with a history of cesarean section, abnormal migration of the placenta to deeper than usual planes in the uterine wall is possible (5). PAS is a severe complication of pregnancy associated with massive and life-threatening bleeding and has become one of the main causes of emergency hysterectomy (6).

Traditional classification

PAS has traditionally been classified based on the degree of penetration of the placenta into the myometrium (7). Therefore, only through the analysis of the post-hysterectomy uterus it's possible to know where the patient was classified into. Due of the limitations of the histology-based approach of the traditional classification, some clinical criteria have been included, obtained during the laparotomy, proposed by FIGO (7). Something similar has been previously described by Collins et al (8). Those findings are not necessarily related to surgical difficulty and expected bleeding volume. Some authors indicate that those kinds of findings can be observed even in the absence of PAS since they are present in cases of uterine dehiscence with placenta previa (9).

Table 1. General classification of PAS (FIGO)

Grade 1 Abnormally Adhered Placenta
	
Clinical criteria Vaginal delivery
 
 ● There is no separation with synthetic oxytocin and controlled cord traction.
---	--

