In centers using the PAS topographic classification and individualized surgical management according to the severity of the lesion, up to 80% of cases can be managed with uterine-sparing surgery without increasing the volume of blood loss (1). The PAS topographic classification has been used in retrospective studies in low- and middle-income countries (1,4) that correlates with clinical outcomes that justifies specific surgical interventions in selected cases. For example, it has been found that type 1 classification, which is the most frequent, is associated with less bleeding and a higher uterine preservation rate; while the types that include low parametrial invasion and invasion of the bladder trigone do not exceed 10% of cases and are linked to increased bleeding and higher surgical challenges (1).

It should be noted that the available literature describing the relationship between topographic classification and its correlation with clinical outcomes is scarce, so it is considered essential to evaluate this classification in a prospective multicentric study that assesses its validity and correlation to surgical difficulty and

clinical outcomes, which could determine the usefulness of the classification in the clinical setting.

JUSTIFICATION FOR THE STUDY

This research aims to evaluate the usefulness of the topographic classification of PAS. Although the classification is based on intraoperative findings and recognizes the particularities within each case of PAS, which has shown correlation to surgical difficulty and the effectiveness of one or another treatment option. To date there are no prospective multicentric studies that deepen and provide further strength to the above associations. In addition, the ease of its application and the acceptability of its use by the obstetrician-gynecologists physicians who use it, is yet unknown.

The topographic classification recognizes the pelvic anatomy and specially the arterial pedicles that irrigate each part of the uterus. It can be applied before incising the uterus and causing bleeding, enables a smooth decision-making process to choose the most appropriate surgical technique for each case, as well as the need for specific vascular interventions. Confirming its usefulness in different countries will facilitate its use by interdisciplinary teams dedicated to the management of PAS at the international level.

RESEARCH QUESTION

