Is the topographic classification of placenta accreta spectrum useful in determining possible clinical outcomes? How acceptable it is by obstetrician-gynecologists who manage PAS?

RESEARCH HYPOTHESES

The topographic classification of placenta accreta spectrum is useful in determining possible clinical outcomes. The topographic classification has high acceptability among obstetrician-gynecologists who manage PAS.

OBJECTIVES

- *General*

To evaluate the clinical outcomes of patients with a diagnosis of placenta accreta spectrum according to the topographic classification, and to explore the acceptability of this classification among obstetrician-gynecologists at the participating medical centers.

- *Specific*

1. To describe the demographic and clinical characteristics of patients with a diagnosis of placenta accreta spectrum.
2. To analyze the clinical outcomes of patients diagnosed with placenta accreta spectrum according to the topographic classification.
3. To explore the acceptability of the topographic classification for placenta accreta spectrum among obstetrician-gynecologists at the participating medical centers.

EXPECTED RESULTS

The aim of this study is to describe the demographic and clinical characteristics of patients with a diagnosis of placenta accreta spectrum, and to determine the correlation between the topographic classification and the clinical outcomes found in the study. Finally, to evaluate whether the proposed classification is accepted by the obstetrician-gynecologists of the participating centers that manage placenta accreta spectrum patients.

METHODOLOGY

Design:

1. Multicentric study of a prospective cohort.

It is clarified that this is an observational study, in which data will be obtained from the medical records and other documents in each participating center, which are considered to be of routine use in day-to-day clinical practice. The study of the outcomes proposed in this protocol will be limited to those recorded in the clinical records and will be taken into account until the participant is discharged

from the hospital, during which a surgical intervention was performed due to the suspicion or diagnosis of PAS.

Study population:

1. Pregnant patients with a diagnosis of placenta accreta spectrum who visits any of the participating medical centers.
2. Obstetrician-gynecologists working in participating medical centers.

Participating centers:

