- b) The following item is added: *The application of the anatomical classification for PAS generates an additional consumption of resources*. It is considered important to ask about that consideration, taking into account that the proposed classification will be very useful in low- and middle-income countries with limited healthcare systems.
- c) Item withdrawn: *The evidence supporting the norm is flawed*, as there are not enough studies addressing the present classification; therefore, it is not relevant to include the item.
- d) The following item is removed: *I am already following another norm or similar strategy*, since this proposed classification has no point of comparison with other types of classifications used in the day-to-day clinical practice.

Descriptive Analysis: Descriptive analysis will be performed using absolute frequencies and calculated percentages of the response option for each item. Finally, the absolute frequencies of each response option will be added up and the response percentage will be calculated to find the global acceptability of the anatomical classification of the placenta accreta spectrum, in relation to what was addressed in the survey.

The results are presented in Table 5.

Table of Variables

Variable Name	Definition	Type of variable	Operational Level	Measure Summary	Objective that resolves
1. Identifier number in the study	Unique consecutive number that identifies the participant in the study	Quantitative	Round numbers starting from 1	NA	NA
2. Date of surgery for PAS treatment	dd/mm/yyyy on which surgical management is performed for the treatment of placental accretism	NA	dd/mm/yy	NA	NA
3. Maternal age	Time in years, from the participant's date of birth to the date of visit, due to suspicion or diagnosis of PAS	Quantitative	Numbers greater ≥ 18	Central tendency and dispersion	1
4. Gravity	Number of pregnancies the patient has had at the time of the first visit for suspected or diagnosed PAS. (Considering the current pregnancy)	Quantitative	Number	Central tendency and dispersion	1
5. Parity	Number of previous deliveries of the patient at the first consultation for suspected or diagnosed PAS.	Quantitative	Number	Central tendency and dispersion	1
6. Previous Cesarean-sections	Number of previous cesarean sections the patient has had until the first visit for suspected or confirmed diagnosis of PAS	Quantitative	Number	Central tendency and dispersion	1

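### Two objection items are dropped from the acceptability survey for reasons the protocol does not support, so two plausible grounds for non-acceptance cannot be recorded directly

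*Combined protocol and SAP*

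**What the plan says.** Under Data Management and Statistical Analysis, Specific Objective 3, the protocol translates an existing instrument for the acceptability of decision rules and lists four adaptations. Change a) replaces the term for the rule throughout. The other three alter the item set:

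- b) adds an item asking whether applying the classification "generates an additional consumption of resources".
- c) withdraws the item stating that the supporting evidence is flawed, "as there are not enough studies addressing the present classification; therefore, it is not relevant to include the item".
- d) withdraws the item stating that the respondent already follows another norm or similar strategy, since "this proposed classification has no point of comparison with other types of classifications used in the day-to-day clinical practice".

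Global acceptability is then formed by adding up the counts of each response option over all items and converting them to percentages, shown in the TOTAL row of Table 5. No reverse coding is described. The matching statement under Research Hypotheses is: "The topographic classification has high acceptability among obstetrician-gynecologists who manage PAS".

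**The concern.** Both withdrawn items are objections, no favourable item is listed as withdrawn, and the hypothesis is that acceptability is high. If the reasons given do not hold, the survey loses two questions that bear directly on whether a physician accepts a new classification: whether the evidence is adequate, and whether the physician already works by something else. Acceptability is one of three specific objectives and half of the stated hypotheses. A result without these questions may look more favourable than the respondents' actual position.

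**Working it through.** **1. Item counts.** Table 5 has 11 statements. Seven are favourable: ease of use, ease of remembering, usefulness, clarity, colleagues' support, patient benefit, better use of resources. Four are objections: lawsuits, a missing clinical detail, the work environment, additional resource consumption. The source instrument is not reproduced in the protocol, so its length is inferred by undoing changes b) to d):

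- Source items: 11 − 1 + 2 = 12.
- Source objections: 4 − 1 + 2 = 5, i.e. 5/12 = 41.7%.
- As adapted: 4/11 = 36.4%.

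Two of five source objections are removed and one new one is added, a net loss of one. The added item concerns resources and does not stand in for either removed topic.

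**2. The reason for d), set beside the rest of the protocol.**

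- The Theoretical Framework (Traditional classification) says "PAS has traditionally been classified based on the degree of penetration of the placenta into the myometrium", and Table 1 sets out the FIGO grades.
- That system is not only histological: "some clinical criteria have been included, obtained during the laparotomy, proposed by FIGO". The Introduction's remark that "its histologic staging is only possible by analyzing a tissue sample after surgery and does not contribute to surgical decisions" therefore covers only its histological part.
- The Theoretical Framework compares the traditional system unfavourably with the topographic one, so a point of comparison is assumed there.
- The withdrawn item also covers any similar strategy. The protocol describes such strategies, for example teams that apply one technique to nearly all their cases.
- Variable 15 in the Table of Variables has a code for surgical technique chosen without the topographic classification. The plan thus allows for this at its own centers.

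**3. The reason for c).** The end of the Theoretical Framework says "the available literature describing the relationship between topographic classification and its correlation with clinical outcomes is scarce", and gives this as the reason for a prospective study. Scarcity of evidence is a matter the item would let physicians judge, so it cannot also make the item irrelevant. A respondent with no view can use the no-opinion column.

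**4. What the total can show.** A fully accepting respondent who gives an opinion on every item agrees with the 7 favourable statements and disagrees with every objection. Under the raw sum, the agree share is:

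- As planned: 7/11 = 63.6%.
- With both items restored (13 items, 6 objections): 7/13 = 53.8%.

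**5. Direction of the effect.** Let p be agreement with favourable items, q with retained objections and r with the two removed objections. The protocol gives none of these. The assumed ranges are p 0.7–0.9, q 0.1–0.3, r 0.1–0.8.

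- Raw: (7p + 4q)/11 as planned, against (7p + 4q + 2r)/13 restored.
- Reverse-scored: (7p + 4(1−q))/11 as planned, against (7p + 4(1−q) + 2(1−r))/13 restored.

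At p = 0.9 and q = 0.1:

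| r | Raw, planned | Raw, restored | Reverse, planned | Reverse, restored |
|---|---|---|---|---|
| 0.1 | 60.9% | 53.1% | 90.0% | 90.0% |
| 0.5 | 60.9% | 59.2% | 90.0% | 83.8% |
| 0.8 | 60.9% | 63.8% | 90.0% | 79.2% |

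Over the whole assumed range, planned minus restored runs from −4.9 to +9.0 percentage points (raw) and from −3.1 to +10.8 points (reverse-scored). Under the raw sum, removal raises the agree share only if r is below (7p + 4q)/11, here 60.9%. A widely endorsed objection would, if removed, lower the raw agree share.

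**The case against.** The reason for d) can be read narrowly, as saying that no comparable classification guides surgery. The protocol offers support: it says FIGO's laparotomy findings need not track surgical difficulty, and that the traditional system gives no ideal management route. Nor does it say that the participating centers use FIGO grading day to day. They are chosen for experience with the topographic system, and only physicians who have applied it are surveyed, so endorsement of d) might be low and its meaning mixed. This weakens the contradiction but does not remove it, because the item also covers other strategies and variable 15 allows for them. A low endorsement would itself be informative.

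A sceptic is not silenced. Such a respondent can disagree that the classification is useful or benefits patients, agree that it misses a clinical detail, or give no opinion. That stands. What is lost is the direct statement of two specific grounds.

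Objective 3 is exploratory and descriptive, with no threshold or test, and the adaptations are disclosed. This limits how serious the point is.

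A reader might infer more than the documents support:

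- **That acceptability is pushed upward.** This is not shown. The scoring direction is not stated, the responses are unknown, and the calculated effect takes either sign.
- **That the edits were made to favour the hypothesis.** The protocol also adds an objection item, and nothing in it shows such a motive.
- **That comparability with other uses of the instrument is lost through these removals.** It is already limited by a direct, unadapted translation and a changed term in every item, and no such comparison is planned.

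**Conclusion.** The concern holds as a matter of justification and coverage. The reason for d) conflicts with the protocol's account of FIGO and with variable 15, and the reason for c) is circular. No item in Table 5 names weak evidence or a competing approach, so neither ground can appear directly in the item-level results, whatever the scoring. This risks overstating acceptability. The shift in the global total cannot be determined: between −4.9 and +10.8 percentage points across both scoring rules, under assumed responses. The count of 5 of 12 objections falling to 4 of 11 rests on the listed changes being complete. It is a modest point, worth acting on because the remedy is cheap.

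**What to change.** 1. Restore both items in the survey and in Table 5, worded for the topographic classification: one on whether its supporting evidence is flawed, one on whether the respondent already follows another classification or similar strategy.
2. Keep the added resource item.
3. Delete the rationale that there is nothing to compare with.
4. Report results item by item. Reverse-code the negatively worded items before forming any global total. Restoring the items without this would lower the ceiling for a fully accepting respondent from 63.6% to 53.8%.
5. The survey is given once, after patient data collection. If it has already been run, state the two removals as a limitation.

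The cost is two more questions, two more table rows and one scoring rule, with possibly a less favourable acceptability result. No patient procedure changes.
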